### 5.5 Supportive Care Guidelines for Immune Related Adverse Events (irAEs)

Adverse events (both non-serious and serious) associated with pembrolizumab exposure may represent an immunologic etiology. These adverse events may occur shortly after the first dose or several months after the last dose of treatment. Pembrolizumab must be withheld for drug-related toxicities and severe or life-threatening AEs as per the Table below. See Section 6.0 for supportive care guidelines, including use of corticosteroids.

Subjects should receive appropriate supportive care measures as deemed necessary by the treating investigator. Suggested supportive care measures for the management of adverse events with potential immunologic etiology are outlined below and in greater detail in the ECI guidance document. Where appropriate, these guidelines include the use of oral or intravenous treatment with corticosteroids as well as additional anti-inflammatory agents if symptoms do not improve with administration of corticosteroids. Note that several courses of steroid tapering may be necessary as symptoms may worsen when the steroid dose is decreased.

If an irAE is suspected, efforts should be made to rule out neoplastic, infectious, metabolic, toxin or other etiologic causes prior to labeling an adverse event as an irAE. Subjects who develop a Grade 2 or higher irAE should be discussed immediately with the overall Principal Investigator or designee. The treatment guidelines are intended to be applied when the investigator determines the events to be related to pembrolizumab.

It may be necessary to perform conditional procedures such as bronchoscopy, endoscopy, or skin photography as part of evaluation of the event. Suggested conditional procedures, as appropriate, can be found in the ECI guidance document.

Note: if after the evaluation the event is determined not to be related, the investigator does not need to follow the treatment guidance (as outlined below). Refer to Section 6.0 for dose modification.

- **Pneumonitis:**
  - For **Grade 2 events**, treat with systemic corticosteroids. When symptoms improve to Grade 1 or less, steroid taper should be started and continued over no less than 4 weeks.
  - For **Grade 3-4 events**, immediately treat with intravenous steroids. Administer additional anti-inflammatory measures, as needed.
  - Add prophylactic antibiotics for opportunistic infections in the case of prolonged steroid administration.
  
- **Type 1 diabetes mellitus (if new onset, including diabetic ketoacidosis [DKA]) or ≥ Grade 3 Hyperglycemia, if associated with ketosis (ketonuria) or metabolic acidosis (DKA)**
  - For **T1DM or Grade 3-4 Hyperglycemia**
    - Insulin replacement therapy is recommended for Type I diabetes mellitus and for Grade 3-4 hyperglycemia associated with metabolic acidosis or ketonuria.
    - Evaluate patients with serum glucose and a metabolic panel, urine ketones, glycosylated hemoglobin, and C-peptide.
  
- **Hypophysitis:**
  - For **Grade 2 events**, treat with corticosteroids. When symptoms improve to Grade 1 or less, steroid taper should be started and continued over no less than 4 weeks. Replacement of appropriate hormones may be required as the steroid dose is tapered.
  - For **Grade 3-4 events**, treat with an initial dose of IV corticosteroids followed by oral corticosteroids. When symptoms improve to Grade 1 or less, steroid taper should be started and continued over no less than 4 weeks. Replacement of appropriate hormones may be required as the steroid dose is tapered.
  
- **Hyperthyroidism or Hypothyroidism:**

Thyroid disorders can occur at any time during treatment. Monitor patients for changes in thyroid function (at the start of treatment, periodically during treatment, and as indicated based on clinical evaluation) and for clinical signs and symptoms of thyroid disorders.

  - **Grade 2 hyperthyroidism events (and Grade 2-4 hypothyroidism):**

- In hyperthyroidism, non-selective beta-blockers (e.g. propranolol) are suggested as initial therapy.
- In hypothyroidism, thyroid hormone replacement therapy, with levothyroxine or liothyronine, is indicated per standard of care.
- **Grade 3-4 hyperthyroidism**
  - Treat with an initial dose of IV corticosteroid followed by oral corticosteroids. When symptoms improve to Grade 1 or less, steroid taper should be started and continued over no less than 4 weeks. Replacement of appropriate hormones may be required as the steroid dose is tapered.
- **Hepatic:**
  - For **Grade 2** events, monitor liver function tests more frequently until returned to baseline values (consider weekly).
    - Treat with IV or oral corticosteroids
  - For **Grade 3-4** events, treat with intravenous corticosteroids for 24 to 48 hours.
  - When symptoms improve to Grade 1 or less, a steroid taper should be started and continued over no less than 4 weeks.
- **Renal Failure or Nephritis:**
  - For **Grade 2** events, treat with corticosteroids.
  - For **Grade 3-4** events, treat with systemic corticosteroids.
  - When symptoms improve to Grade 1 or less, steroid taper should be started and continued over no less than 4 weeks.
- **Cerebral Edema**

Due to the immunologic nature of pembrolizumab administration, cerebral edema could theoretically result as a consequence of pembrolizumab administration due to immune infiltration of the brain. Symptoms related to cerebral edema may include headache or neurologic deficit that is either new or worsened. Patients with any signs or symptoms of cerebral edema should be treated as clinically appropriate including initiation or increased systemic corticosteroid dosing, treatment with an osmotic diuretic or surgical decompression. Subsequent pembrolizumab dosing should be immediately interrupted if significant clinical symptoms attributable to cerebral edema develop. Treatment with additional pembrolizumab doses may only be re-initiated if clinically significant symptoms attributable to cerebral edema have resolved to grade  $\leq 1$  or pre-treatment baseline. Patients who develop CTCAE 4.0 grade-4 cerebral edema attributable to pembrolizumab administration should not receive further pembrolizumab doses and should discontinue study therapy.

Recommendations to manage irAEs not detailed elsewhere in the protocol are detailed in Table 4.

Table 4 Dose Modification and Toxicity Management Guidelines for Immune-related AEs Associated with Pembrolizumab

**General instructions:**

1. Corticosteroid taper should be initiated upon AE improving to Grade 1 or less and continue to taper over at least 4 weeks.
2. For situations where pembrolizumab has been withheld, pembrolizumab can be resumed after AE has been reduced to Grade 1 or 0 and corticosteroid has been tapered. Pembrolizumab should be permanently discontinued if AE does not resolve within 12 weeks of last dose or corticosteroids cannot be reduced to  $\leq 10$  mg prednisone or equivalent per day within 12 weeks.
3. For severe and life-threatening irAEs, IV corticosteroid should be initiated first followed by oral steroid. Other immunosuppressive treatment should be initiated if irAEs cannot be controlled by corticosteroids.

Immune-related AEs	Toxicity grade or conditions (CTCAEv 4.0)	Action taken to pembrolizumab	irAE management with corticosteroid and/or other therapies	Monitor and follow-up
Pneumonitis	Grade 2	Withhold	
 
• Administer corticosteroids (initial dose of 1-2 mg/kg prednisone or equivalent) followed by taper
 
	
 
• Monitor participants for signs and symptoms of pneumonitis
 
• Evaluate participants with suspected pneumonitis with radiographic imaging and initiate corticosteroid treatment
 
• Add prophylactic antibiotics for opportunistic infections
 

	Grade 3 or 4, or recurrent Grade 2	Permanently discontinue		
Diarrhea / Colitis	Grade 2 or 3	Withhold	
 
• Administer corticosteroids (initial dose of 1-2 mg/kg prednisone or equivalent) followed by taper
 
	
 
• Monitor participants for signs and symptoms of enterocolitis (ie, diarrhea, abdominal pain, blood or mucus in stool with or without fever) and of bowel perforation (ie, peritoneal signs and ileus).
 
• Participants with <math>\geq</math> Grade 2 diarrhea suspecting colitis should consider GI consultation and performing endoscopy to rule out colitis.
 
• Participants with diarrhea/colitis should be advised to drink liberal quantities of clear fluids. If sufficient oral fluid intake is not feasible, fluid and electrolytes should be substituted via IV infusion.
 

	Grade 4	Permanently discontinue		
AST / ALT elevation or Increased bilirubin	Grade 2	Withhold	
 
• Administer corticosteroids (initial dose of 0.5- 1 mg/kg prednisone or equivalent) followed by taper
 
	
 
• Monitor with liver function tests (consider weekly or more frequently until liver enzyme value returned to baseline or is stable)
 

	Grade 3 or 4	Permanently discontinue	
 
• Administer corticosteroids (initial dose of 1-2 mg/kg prednisone or
 
	

			equivalent) followed by taper	
Type 1 diabetes mellitus (T1DM) or Hyperglycemia	Newly onset T1DM or Grade 3 or 4 hyperglycemia associated with evidence of $\beta$ -cell failure	Withhold	
 
Initiate insulin replacement therapy for participants with T1DM
 
Administer anti-hyperglycemic in participants with hyperglycemia
 
	
 
Monitor participants for hyperglycemia or other signs and symptoms of diabetes.
 

Hypophysitis	Grade 2	Withhold	
 
Administer corticosteroids and initiate hormonal replacements as clinically indicated.
 
	
 
Monitor for signs and symptoms of hypophysitis (including hypopituitarism and adrenal insufficiency)
 

	Grade 3 or 4	Withhold or permanently discontinue 		
Hyperthyroidism	Grade 2	Continue	
 
Treat with non-selective beta-blockers (eg, propranolol) or thionamides as appropriate
 
	
 
Monitor for signs and symptoms of thyroid disorders.
 

	Grade 3 or 4	Withhold or permanently discontinue 		
Hypothyroidism	Grade 2-4	Continue	
 
Initiate thyroid replacement hormones (eg, levothyroxine or liothyronine) per standard of care
 
	
 
Monitor for signs and symptoms of thyroid disorders.
 

Nephritis and Renal dysfunction	Grade 2	Withhold	
 
Administer corticosteroids (prednisone 1-2 mg/kg or equivalent) followed by taper.
 
	
 
Monitor changes of renal function
 

	Grade 3 or 4	Permanently discontinue		
Myocarditis	Grade 1 or 2	Withhold	
 
Based on severity of AE administer corticosteroids
 
	
 
Ensure adequate evaluation to confirm etiology and/or exclude other causes
 

	Grade 3 or 4	Permanently discontinue		
All other immune-related AEs	Intolerable/persistent Grade 2	Withhold	
 
Based on type and severity of AE administer corticosteroids
 
	
 
Ensure adequate evaluation to confirm etiology and/or exclude other causes
 

	Grade 3	Withhold or discontinue based on the type of event. Events that require discontinuation include and not limited to: Guillain-Barre		

		Syndrome, encephalitis		
	Grade 4 or recurrent Grade 3	Permanently discontinue		

1. Withhold or permanently discontinue pembrolizumab is at the discretion of the investigator or treating physician.
 
NOTE:          For participants with Grade 3 or 4 immune-related endocrinopathy where withhold of pembrolizumab is required, pembrolizumab may be resumed when AE resolves to <math>\leq</math> Grade 2 and is controlled with hormonal replacement therapy or achieved metabolic control (in case of T1DM).
				

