#### **5.4 General Concomitant Medication and Supportive Care Guidelines**

Medications or vaccinations specifically prohibited in the exclusion criteria are not allowed during the ongoing trial. If there is a clinical indication for one of these or other medications or vaccinations specifically prohibited during the trial, discontinuation from trial therapy or vaccination may be required. The investigator should discuss any questions regarding this with the Merck Clinical team. The final decision on any supportive therapy or vaccination rests with the investigator and/or the subject's primary physician.

- **Diarrhea/Colitis:**  
Subjects should be carefully monitored for signs and symptoms of enterocolitis (such as diarrhea, abdominal pain, blood or mucus in stool, with or without fever) and of bowel perforation (such as peritoneal signs and ileus).
  - All subjects who experience diarrhea/colitis should be advised to drink liberal quantities of clear fluids. If sufficient oral fluid intake is not feasible, fluid and electrolytes should be substituted via IV infusion. For Grade 2 or higher diarrhea, consider GI consultation and endoscopy to confirm or rule out colitis.
  - For **Grade 2 diarrhea/colitis** that persists greater than 3 days, administer oral corticosteroids.
  - For **Grade 3 or 4 diarrhea/colitis** that persists > 1 week, treat with intravenous steroids followed by high dose oral steroids.
  - When symptoms improve to Grade 1 or less, steroid taper should be started and continued over no less than 4 weeks.
- **Nausea/vomiting:** Nausea and vomiting should be treated aggressively, and consideration should be given in subsequent cycles to the administration of prophylactic antiemetic therapy according to standard institutional practice. Subjects should be strongly encouraged to maintain liberal oral fluid intake.
- **Anti-infectives:** Subjects with a documented infectious complication should receive oral or IV antibiotics or other anti-infective agents as considered appropriate by the treating investigator for a given infectious condition, according to standard institutional practice.
- Immune-related adverse events: See Section 6.0 and Events of Clinical Interest Guidance Document for supportive care guidelines, including use of corticosteroids, regarding diagnosis and management of adverse experiences of a potential immunologic etiology.

**Management of Infusion Reactions:** Signs and symptoms usually develop during or

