## 6. DOSING DELAYS/DOSE MODIFICATIONS

The descriptions and grading scales found in the revised NCI Common Terminology Criteria for Adverse Events (CTCAE) version 4.0 will be utilized for dose delays and dose modifications. A copy of the CTCAE version 4.0 can be downloaded from the CTEP website.

[http://ctep.cancer.gov/protocolDevelopment/electronic\\_applications/ctc.htm](http://ctep.cancer.gov/protocolDevelopment/electronic_applications/ctc.htm).

Pembrolizumab will be withheld for drug-related Grade 4 hematologic toxicities, non-hematological toxicity  $\geq$  Grade 3 including laboratory abnormalities despite appropriate replacement therapies when appropriate, and severe or life-threatening AEs as per Table 5.

Table 5 Dose modification guidelines for drug-related adverse events

Toxicity	Hold Treatment For Grade	Timing for Restarting Treatment	Treatment Discontinuation
Diarrhea/Colitis	2-3	Toxicity resolves to Grade 0-1	Toxicity does not resolve within 12 weeks of last dose or inability to reduce corticosteroid to 10 mg or less of prednisone or equivalent per day within 12 weeks
	4	Permanently discontinue	Permanently discontinue
AST, ALT, or Increased Bilirubin	2	Toxicity resolves to Grade 0-1	Toxicity does not resolve within 12 weeks of last dose
	3-4	Permanently discontinue (see exception below) a	Permanently discontinue
Type 1 diabetes mellitus (if new onset) or Hyperglycemia	T1DM or 3-4	Hold pembrolizumab for new onset Type 1 diabetes mellitus or Grade 3-4 hyperglycemia associated with evidence of beta cell failure	Resume pembrolizumab when patients are clinically and metabolically stable
Hypophysitis	2-4	Toxicity resolves to Grade 0-1. Therapy with pembrolizumab can be continued while endocrine replacement therapy is instituted	Toxicity does not resolve within 12 weeks of last dose or inability to reduce corticosteroid to 10 mg or less of prednisone or equivalent per day within 12 weeks
Hyperthyroidism	3	Toxicity resolves to Grade 0-1	Toxicity does not resolve within 12 weeks of last dose or inability to reduce corticosteroid to 10 mg or less of prednisone or equivalent per day within 12 weeks
	4	Permanently discontinue	Permanently discontinue
Hypothyroidism		Therapy with pembrolizumab can be continued while thyroid replacement therapy is instituted	Therapy with pembrolizumab can be continued while thyroid replacement therapy is instituted

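### For five steroid-treated immune events, Table 5 allows pembrolizumab to restart at Grade 0-1 alone, while Table 4 also requires the corticosteroid to have been tapered

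*Combined protocol and SAP*

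**What the plan says.** Table 4 (Section 5.5) opens with general instructions for every event in it. Instruction 1 reads "Corticosteroid taper should be initiated upon AE improving to Grade 1 or less and continue to taper over at least 4 weeks". Instruction 2 says that, where drug was withheld, "pembrolizumab can be resumed after AE has been reduced to Grade 1 or 0 and corticosteroid has been tapered". Restart therefore has two conditions, on grade and on steroid. Instruction 2 also stops treatment for good if the event has not resolved, or prednisone is not down to 10 mg/day, within 12 weeks.

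The narrative sections give the same taper trigger. Section 5.4 says for colitis "When symptoms improve to Grade 1 or less, steroid taper should be started and continued over no less than 4 weeks", and Section 5.5 says for hepatic events "When symptoms improve to Grade 1 or less, a steroid taper should be started and continued over no less than 4 weeks". Section 5.5 has equivalent wording for pneumonitis, hypophysitis and nephritis.

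Table 5 (Section 6) has its own restart column. For colitis, Grade 2 AST/ALT/bilirubin, pneumonitis, nephritis and hypophysitis the condition is "Toxicity resolves to Grade 0-1". The hypophysitis cell adds "Therapy with pembrolizumab can be continued while endocrine replacement therapy is instituted". Corticosteroid appears in Section 6 only in the discontinuation column, as the 12-week, 10 mg/day limit. The Grade 2 AST/ALT/bilirubin row does not have that limit.

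**The concern.** Reaching Grade 1 does two different things. In Table 4 it starts a steroid taper of at least 4 weeks, and restart waits for the taper. In Table 5 it is the whole restart condition. A site that reads Section 6 as written could re-expose a patient to pembrolizumab just as the taper begins, which Table 4 does not allow.

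What is at stake is consistent and safe re-dosing after immune toxicity. Two sites, or one site on two occasions, could treat the same event differently and each cite the protocol. The missing hepatic limit has a similar effect: under Table 5 alone, a patient whose liver tests recover but who cannot come off high-dose steroid has no stated stopping rule, whereas under Table 4 that patient stops.

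**Working it through.** **Step 1. The two tables row by row.**

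| Event withheld in both tables | Table 4: restart needs | Table 5: restart needs | 10 mg/12-week limit in Table 5 discontinuation cell |
|---|---|---|---|
| Colitis, Grade 2-3 | Grade 0-1 and steroid tapered | Grade 0-1 | Yes |
| AST/ALT/bilirubin, Grade 2 | Grade 0-1 and steroid tapered | Grade 0-1 | No |
| Pneumonitis, Grade 2 | Grade 0-1 and steroid tapered | Grade 0-1 | Yes |
| Nephritis, Grade 2 | Grade 0-1 and steroid tapered | Grade 0-1 | Yes |
| Hypophysitis, Grade 2 | Grade 0-1 and steroid tapered | Grade 0-1; may continue with hormone replacement | Yes |

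All five differ in the restart condition. Hypophysitis belongs here because Table 4 treats it with steroid: "Administer corticosteroids and initiate hormonal replacements as clinically indicated". At Grade 3-4 it falls under the NOTE below Table 4, which has its own rule for endocrinopathies (Grade 2 or less with hormonal control), so the comparison is limited to Grade 2. The catch-all Grade 3 rows show the same gap for immune events other than endocrinopathies.

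**Step 2. Time scale.** The minimum taper is 4 x 7 = 28 days and a cycle is 21 days (Section 5.1). A completed taper cannot fit inside one cycle.

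**Step 3. Illustration: Grade 1 reached before the next scheduled dose.** From Table 4: starting prednisone of 1-2 mg/kg for colitis, pneumonitis and nephritis, and "initial dose of 0.5- 1 mg/kg prednisone or equivalent" for Grade 2 hepatic events. Table 4 gives no dose for hypophysitis, so none is computed. Assumptions: 70 kg; linear 28-day taper from the starting dose to zero; Grade 1 reached on cycle day r, from 1 to 21; next dose on Day 22. Starting doses are then 70-140 mg, and 35-70 mg for hepatic events.

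Dose at Day 22 = start x (1 - (22 - r)/28):

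- 70 mg: 17.5 mg (r = 1) to 67.5 mg (r = 21)
- 140 mg: 35 mg to 135 mg
- 35 mg: 8.75 mg to 33.75 mg

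Delay under Table 4, if the cycle can be re-timed (Section 8.7 allows longer intervals for toxicity):

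- Tapered means completed: (r + 28) - 22 = r + 6, so 7 to 27 days.
- Tapered means 10 mg/day or less: days to reach 10 mg = 28 x (1 - 10/start) = 20 (35 mg), 24 (70 mg), 26 (140 mg). Delay = max(0, r + that - 22): 3 to 25 days for 1-2 mg/kg starts, and 0 to 23 days for hepatic events.

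The low ends use r = 1, where onset, treatment and improvement all fall on the day of the last dose. That is not realistic. For colitis, Section 5.4 starts steroid only after Grade 2 has lasted more than 3 days.

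**Step 4. Illustration: event still above Grade 1 on Day 22.** This is the ordinary held dose. If Table 5 is applied on the day Grade 1 is reached, the patient is re-dosed at the start of the taper, at 35-140 mg/day under the same assumptions. Table 4 puts restart 28 days later if the taper must be completed, or 20, 24 or 26 days later (starts of 35, 70 and 140 mg) if 10 mg/day is enough.

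**Step 5. The 12-week limit.** In Step 3, with the last dose on Day 1, the latest taper ends on day 21 + 28 = 49, and 12 weeks end on day 1 + 84 = 85. Waiting for the taper does not by itself force discontinuation in those cases.

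The taper length is a minimum, so none of these figures is a bound.

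**The case against.** The best counter-argument is that the protocol already ranks the tables. Section 5.1 places dose modification in Section 6, Section 5.5 refers there too, and the sentence directly above Table 4 presents it as covering immune events that the rest of the protocol leaves out. On that reading Table 5 governs. The pointers do lean that way, but they do not settle restart. Section 5.5 also tells sites to withhold drug according to the table that follows it, which is Table 4. Table 4 is titled as dose modification guidance and has its own rows for all five events, so its restart rule would have no effect on events that it names. The same sentence can also be read as letting Table 4 supply the taper condition that Table 5 leaves out.

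Second, Table 5 is silent on the taper and does not tell anyone to restart during it. For the five events a site that follows Table 4 satisfies both tables. That stands, and a reader who infers that the two rules cannot both be met would be wrong. But the Table 5 column sets out when treatment may restart and gives one condition only.

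Third, four of the five Table 5 rows carry the 10 mg/12-week limit. That limit says when to stop for good. It does not say when restart is allowed.

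Fourth, Section 5.5 requires Grade 2 or higher immune events to be discussed at once with the overall principal investigator. This limits variation, but that investigator has the same two written rules. Appendix B, the event guidance document, is visible only as a heading and may address restart timing.

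**Conclusion.** The inconsistency is real for the five events and is minor. Confidence is high on the difference in wording. It is lower on whether any governing rule exists, because Appendix B cannot be read. The firm size statement is that the minimum taper (28 days) is longer than a cycle (21 days). The mg/day and delay figures rest on assumed body weight, taper shape and timing, and only illustrate the gap. For hepatic events that start at 0.5 mg/kg the gap can be small.

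Three stronger readings are not supported. A reader might infer that patients will be harmed, but the documents give no frequency for these events and no evidence on recurrence after early restart. A reader might infer that Table 4 is stricter throughout, but its NOTE lets Grade 3-4 endocrinopathies restart at Grade 2 or less, which is looser on grade than Table 5. A reader might infer that the trial's conclusion is at risk, but the 6-month PFS endpoint, the sample size and the decision rule do not depend on this.

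**What to change.** In Section 6, state that for immune-related events treated with corticosteroid, pembrolizumab restarts only when the event is at Grade 0-1 and the steroid given for it has been tapered, as in Table 4 instruction 2. Except Grade 3-4 endocrinopathies, which follow the Table 4 NOTE.

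Add the taper condition to six Table 5 restart cells: colitis, Grade 2 AST/ALT/bilirubin, Grade 2 pneumonitis, Grade 2 nephritis, hypophysitis (Grade 2 only, keeping the hormone-replacement sentence), and all other drug-related toxicity where it is immune-related and not an endocrinopathy.

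Define tapered once. Prednisone or equivalent at 10 mg/day or less is the threshold the protocol already uses. Without a definition, the edit would copy the present ambiguity into six cells.

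Add the 10 mg/12-week limit to the Grade 2 AST/ALT/bilirubin discontinuation cell.

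The cost is an amendment with one governing sentence, one definition and seven cell edits. It needs no new data, visits or patients. The downside is that sites now working from Table 5 alone would restart some patients later, by up to the length of the taper.

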Infusion Reaction	2 b	Toxicity resolves to Grade 0-1	Permanently discontinue if toxicity develops despite adequate premedication
	3-4	Permanently discontinue	Permanently discontinue
Pneumonitis	2	Toxicity resolves to Grade 0-1	Toxicity does not resolve within 12 weeks of last dose or inability to reduce corticosteroid to 10 mg or less of prednisone or equivalent per day within 12 weeks

Toxicity	Hold Treatment For Grade	Timing for Restarting Treatment	Treatment Discontinuation
	3-4	Permanently discontinue	Permanently discontinue
Renal Failure or Nephritis	2	Toxicity resolves to Grade 0-1	Toxicity does not resolve within 12 weeks of last dose or inability to reduce corticosteroid to 10 mg or less of prednisone or equivalent per day within 12 weeks
	3-4	Permanently discontinue	Permanently discontinue
All Other Drug-Related Toxicity c	3 or Severe	Toxicity resolves to Grade 0-1	Toxicity does not resolve within 12 weeks of last dose or inability to reduce corticosteroid to 10 mg or less of prednisone or equivalent per day within 12 weeks
	4	Permanently discontinue	Permanently discontinue

Note: Permanently discontinue for any severe or Grade 3 drug-related AE that recurs or any life-threatening event.
 
a For patients with liver metastasis who begin treatment with Grade 2 AST or ALT, if AST or ALT increases by greater than or equal to 50% relative to baseline and lasts for at least 1 week then patients should be discontinued.
 
b If symptoms resolve within one hour of stopping drug infusion, the infusion may be restarted at 50% of the original infusion rate (e.g., from 100 mL/hr to 50 mL/hr). Otherwise dosing will be held until symptoms resolve and the subject should be premedicated for the next scheduled dose; Refer to
 
Table – Infusion Treatment Guidelines for further management details.
 
c Patients with intolerable or persistent Grade 2 drug-related AE may hold study medication at physician discretion. Permanently discontinue study drug for persistent Grade 2 adverse reactions for which treatment with study drug has been held, that do not recover to Grade 0-1 within 12 weeks of the last dose.
			

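### Tables 4 and 5 give opposite instructions after a first Grade 3 myocarditis (and Grade 3 Guillain-Barré syndrome or encephalitis), and Section 6 does not say which table governs

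*Combined protocol and SAP*

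**What the plan says.** **Section 5.5, Table 4** is the dosing and management table for immune-related adverse events (irAEs). Drug is withheld for myocarditis at Grade 1 or 2 and permanently discontinued at Grade 3 or 4. In the row for all other irAEs, Grade 3 is withhold or discontinue according to the type of event, and Guillain-Barré syndrome and encephalitis are named as events that require discontinuation. Where drug has been withheld, general instruction 2 says that "pembrolizumab can be resumed after AE has been reduced to Grade 1 or 0 and corticosteroid has been tapered". It adds: "Pembrolizumab should be permanently discontinued if AE does not resolve within 12 weeks of last dose".

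The table is introduced with: "Recommendations to manage irAEs not detailed elsewhere in the protocol are detailed in Table 4". Earlier in Section 5.5, a sentence makes withholding for drug-related toxicity follow the table below it, and a Note ends: "Refer to Section 6.0 for dose modification".

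**Section 6, Table 5** is the dosing table for drug-related adverse events in general. Its opening rule withholds drug for drug-related non-hematological toxicity of Grade 3 or higher, "and severe or life-threatening AEs as per Table 5". Table 5 has no row for myocarditis, Guillain-Barré syndrome or encephalitis. The row "All Other Drug-Related Toxicity" holds at Grade 3 or severe, restarts when toxicity resolves to Grade 0-1, and stops drug permanently at Grade 4. The note below the table reads: "Permanently discontinue for any severe or Grade 3 drug-related AE that recurs or any life-threatening event". Footnote c leaves a Grade 2 hold to the physician, and only for intolerable or persistent events.

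**The concern.** A myocarditis that the investigator attributes to pembrolizumab is both an irAE (Table 4) and a drug-related toxicity (Table 5). For a first Grade 3 event that is not life-threatening, one table ends treatment and the other allows it to resume after recovery. Two investigators following the protocol in good faith could therefore act in opposite ways. What is at stake is re-exposure of a patient to the drug suspected of causing a severe cardiac or neurological event, and consistent handling across sites.

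**Working it through.** No arithmetic is involved beyond counting rows, and the plan states no figure to reproduce. The check sets the two tables side by side.

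**1. First myocarditis event, by grade**

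| Grade | Table 4, myocarditis row | Table 5, residual row with note and footnote c | Same action? |
|---|---|---|---|
| 1 | Withhold | No hold | No |
| 2 | Withhold | Hold only if intolerable or persistent, at physician discretion | No |
| 3 | Permanently discontinue | Hold; restart at Grade 0-1 | No, opposite |
| 4 | Permanently discontinue | Permanently discontinue | Yes |

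**2. Does the Table 5 note close the Grade 3 gap?** No.

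- It stops drug for a severe or Grade 3 event that recurs, so a first event is outside that clause. Reading the recurrence condition as attached only to Grade 3, so that any severe event is a stop, would contradict the residual row, which lets events that are Grade 3 or severe restart.
- It also stops drug for a life-threatening event. Section 7.5, Table 6 grades an event that is severe but not immediately life-threatening as Grade 3, and life-threatening consequences as Grade 4. An ordinary Grade 3 event is therefore not caught.
- The remaining Table 5 limit is a permanent stop if toxicity has not resolved within 12 weeks of the last dose, or if corticosteroid cannot be reduced to 10 mg prednisone equivalent or less per day in that time. A patient who recovers in time may restart.

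**3. How far does the mismatch extend?** Conditions for which Table 4 requires a permanent stop at Grade 3:

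- In a row of their own: pneumonitis, AST/ALT or bilirubin elevation, nephritis, myocarditis = 4.
- Named inside the row for all other irAEs: Guillain-Barré syndrome, encephalitis = 2.
- Total named: 4 + 2 = 6.
- With a Table 5 row giving the same Grade 3 stop: pneumonitis, AST/ALT or bilirubin (with the liver-metastasis exception in footnote a), renal failure or nephritis = 3.
- Without one: 6 − 3 = 3, namely myocarditis, Guillain-Barré syndrome and encephalitis.

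Table 4 says that its list inside that last row is not exhaustive, so 6 counts only what is named.

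**4. Does Section 6 yield to Table 4?** It contains no sentence that does so. Its opening rule applies on its own terms to drug-related toxicity and cites Table 5. Section 5.5 applies its guidance to events judged related to pembrolizumab, so the same event falls under both.

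**The case against.** The strongest reply is that the protocol, read as a whole, already sends these events to Table 4. Section 5.5 ties withholding to the table that follows it, which is Table 4. The sentence introducing Table 4 assigns to it irAEs not detailed elsewhere, and myocarditis is named nowhere in Table 5. A named row is more specific than a residual one. All of this stands, and Table 4 is very probably what the sponsor intends.

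A reader might take the Section 5.5 sentence "Refer to Section 6.0 for dose modification" as an order to leave Table 4 for Table 5. It does not support that. It closes a Note about events judged not related to the drug. The conflict rests instead on Section 6's own opening rule and Table 5.

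There are also safeguards. Section 5.5 says: "Subjects who develop a Grade 2 or higher irAE should be discussed immediately with the overall Principal Investigator or designee". That covers every Grade 3 case. Table 6 requires advance approval of rechallenge after a serious event possibly caused by the drug, but refers back to the protocol's dose modification guidelines. Section 5.12 requires the Overall PI to be told of unusual or life-threatening complications. These make a mistaken restart less likely, but none says which table decides. Appendix B, the guidance on events of clinical interest, is listed but was not available for this check, so whether it addresses myocarditis is unknown.

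A reader might also infer that the Grade 1 myocarditis hold is empty, because general instruction 2 allows restart at Grade 1. The wording does not establish that. It speaks of an event that has been reduced, it permits restart without requiring it, and the next sentence stops drug if the event does not resolve within 12 weeks. An event that starts and stays at Grade 1 has arguably not been reduced. This is at most an ambiguity.

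**Conclusion.** Wrong as written: an internally contradictory dosing rule. At Grade 3, Table 4 stops drug permanently for myocarditis, Guillain-Barré syndrome and encephalitis, while Table 5 allows restart after a first event that is not life-threatening. For myocarditis the tables also differ at Grades 1 and 2. The text favours Table 4, so the defect is that Section 6 neither repeats the stop nor defers to it.

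This assumes that the event is judged drug-related and is not life-threatening, and that Appendix B does not settle the matter.

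Three stronger inferences are not supported. Myocarditis is not the only condition affected. The documents give no myocarditis frequency, so no number of patients or doses can be attached. No effect on PFS6 or on the proportions with Grade 3 or higher hematologic or neurologic toxicity is claimed: neither definition depends on which table is followed, and a patient with a Grade 3 neurologic event is counted under either.

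**What to change.** In Section 6, with Table 5:

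1. Add a precedence sentence: *For immune-related AEs listed in Table 4 without a dedicated row in Table 5, Table 4 governs.* This leaves every existing dedicated row in Table 5 untouched.
2. Add a myocarditis row matching Table 4: withhold at Grade 1-2, with the restart and 12-week limits of Table 4's general instruction 2; permanently discontinue at Grade 3-4.
3. Name Guillain-Barré syndrome and encephalitis in Table 5 as permanent stops at Grade 3.

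The cost is one sentence, one row and two named events in an amendment, with no added patients, visits or tests. A patient who recovers from a first Grade 3 event of these kinds loses the restart that Table 5 now appears to allow, which Table 4 already rules out.

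Separately, the sponsor may wish to say whether myocarditis that begins and remains at Grade 1 can restart at that grade under general instruction 2. That is a clinical choice, and no Grade 0 requirement is asked for. Such a rule would hold a Grade 1 event to a stricter standard than a Grade 2 event, which may restart at Grade 1.
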